This study aims to explore the potential of an aerobic exercise program on brain structure and function in MS in a single-blind, randomized controlled phase IIa trial. We hypothesize that exercise will improve verbal learning and memory (primary endpoint) as well as induce changes in neuroimaging markers of structural and functional CNS connectivity (secondary endpoints). Tertiary outcomes will include walking ability, motor function and coordination, as well as patient-based outcomes (depression, fatigue, and health-related quality of life).

8 Trial design: Description of trial design including type of trial (eg, parallel group, crossover, factorial, single group), allocation ratio, and framework (eg, superiority, equivalence, noninferiority, exploratory)

This is a single-blind, randomized, controlled phase IIa trial with a parallel group design comparing 3 months of standardized aerobic exercise training (bicycle ergometry) to a waitlist control group (superiority framework). The allocation ratio of exercise to waitlist control is 1:1. The trial consists of a **primary trial phase** and an **extension phase** (see Figure 1). All primary analyses of endpoints will be restricted to the primary trial phase.

All outcome parameters will be assessed at baseline (week 0), after the intervention (month 3), and at follow-up (month 6), see Figure 1. Each outcome

assessment block (blue rectangles) includes: Clinical assessment (neurological scoring and neuropsychological testing), magnetic resonance imaging (structural and functional MRI), magnetencephalography (MEG), and assessments of physical fitness at the Department of Sports Medicine. After completing Month 3 assessments, patients randomized to the WLC will be offered the aerobic exercise training program and patients in the training group will be offered to continue the training free of charge (extension phase).

III) Methods: Participants, interventions, and outcomes

9 Study setting: Description of study settings (e.g., community clinic, academic hospital) and list of countries where data will be collected. Reference to where list of study sites can be obtained

This single-center study will be conducted at the University-Medical Center

Hamburg Eppendorf (UKE).

10 Eligibility criteria: Inclusion and exclusion criteria for participants. If applicable, eligibility criteria for study centers and individuals who will perform the interventions (e.g., surgeons, psychotherapists)

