12.1. Endpoints

The primary, secondary, and tertiary endpoints of the trial are listed in Table 2 below and described in detail in the following paragraphs. In addition to these endpoints, several ancillary studies will be conducted to maximize the scientific knowledge gained regarding the neurobiological and physiological effects of exercise in patients with MS (see section 12.2.).

Endpoint	Construct	Measure
Primary endpoint	Verbal Learning and Memory	VLMT
Secondary endpoints	Functional connectivity	rs MEG, rs fMRI
	Structural integrity and connectivity	GM density, DTI
	Other cognitive functions	Neuropsych. battery
Tertiary endpoints	Walking ability	6MWT, accelerometry
	Motor coordination and balance	MFT-S3
	Well-being and quality of life	Patient-reported outcomes

Table 2. Overview of primary, secondary, and tertiary endpoints of the AERCONN trial.

12.1.1. Primary endpoint:

The primary endpoint of this study will be the Verbal Learning and Memory Scale (VLMT, Helmstaedter, Lendt and Lux, 2001) after 3 months of training. Learning and

memory are important domains of cognitive function and frequently impaired in MS, with important implications for quality of life, vocational status and psychosocial problems (Chiaravalotti and De Luca, 2008; Langdon, 2011). Moreover, MS patients rank memory and thinking amongst the most important body functions (Heesen et al., Mult Scler 2008).

Learning and memory is among the cognitive domains most consistently shown to improve after aerobic exercise training in numerous studies including patients with chronic diseases and aged healthy individuals (Smith et al., Psychosom Med 2010). Moreover, in our previous pilot trial of aerobic exercise in progressive MS (Briken et al., MSJ 2013), verbal learning and memory as measured by the VLMT was significantly increased after the training program.

12.1.2. Secondary endpoints:

Secondary endpoints include imaging-based measures of brain integrity and connectivity as well as neuropsychological tests covering several domains of higher-order brain function.

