Sample size was calculated based on results obtained in the pilot study on exercise and cognitive function in progressive MS (Briken et al., MSJ 2013). Below are the power calculations for the VLMT learning (trials 1 through 5) and delayed memory (trial 7).

14.1. VLMT Learning:

Numeric Results for Two-Sample T-Test

Null Hypothesis: Mean1=Mean2. Alternative Hypothesis: Mean1<>Mean2

The standard deviations were assumed to be unknown and equal.

Power	N1	N2	Ratio	Alpha	Beta	Mean1	Mean2	S1	S2
0.90388	20	20	1.000	0.02500	0.09612	4.0	9.8	5.0	5.0
0.81609	16	16	1.000	0.02500	0.18391	4.0	9.8	5.0	5.0
0.90639	17	17	1.000	0.05000	0.09361	4.0	9.8	5.0	5.0
0.80985	13	13	1.000	0.05000	0.19015	4.0	9.8	5.0	5.0

Group sample sizes of 20 and 20 achieve 90% power to detect a difference of -5.8 between the null hypothesis that both group means are 4.0 and the alternative hypothesis that the mean of group 2 is 9.8 with estimated group standard deviations of 5.0 and 5.0 and with a significance level (alpha) of 0.02500 using a two-sided two-sample t-test.

14.2. VLMT Delayed recall:

Numeric Results for Two-Sample T-Test

Null Hypothesis: Mean1=Mean2. Alternative Hypothesis: Mean1<>Mean2

The standard deviations were assumed to be unknown and equal.

Power	N1	N2	Ratio	Alpha	Beta	Mean1	Mean2	S1	S2
0.91886	17	17	1.000	0.02500	0.08114	0.6	3.2	2.0	2.0
0.81514	13	13	1.000	0.02500	0.18486	0.6	3.2	2.0	2.0
0.91148	14	14	1.000	0.05000	0.08852	0.6	3.2	2.0	2.0
0.82630	11	11	1.000	0.05000	0.17370	0.6	3.2	2.0	2.0

Group sample sizes of 17 and 17 achieve 92% power to detect a difference of -2.6 between the null hypothesis that both group means are 0.6 and the alternative hypothesis that the mean of group 2 is 3.2 with estimated group standard deviations of 2.0 and 2.0 and with a significance level (alpha) of 0.02500 using a two-sided two-sample t-test.

14.3. Summary statement:

Based on these calculations, powering for the dual primary endpoints VLMT learning and VLMT delayed recall, 90% power will be achieved with n=20 patients in each

arm of the trial. To safeguard against dropouts (based on previous experience, drop-out in behavioral trials often reach 20%) and the possibility that effect sizes in the pilot trial may have overestimated the real effect, we will enrol n=60 patients in the trial so that we will have approximately n=30 in each trial arm.

15 Recruitment: *Strategies for achieving adequate participant enrolment to reach target sample size.*

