Management of screening, inclusion and study conduct will be based on the internet-based project-management tool attached to the HAPIMS database. This database uses secure data management and has been approved for use by the responsible Data Protection and Security Office of the UKE. Data will be collected on paper-based source documents (neuropsychological assessments, performance-based measures, questionnaires) or primary computer-based (MRI, MEG) or chip-based (accelerometry). Data will be uploaded on a protected web-based project-platform to allow an integrated view on all assessments.

Assessment of safety: DSMB reports will be prepared biannually. As we do not expect adverse events DSMB recommendations for taking patients out or stopping the study seem highly unlikely.

18b Retention: Plans to promote participant retention and complete follow-up, including list of any outcome data to be collected for participants who discontinue or deviate from intervention protocols.

See 11c.

19 Data management: *Plans for data entry, coding, security, and storage, including any related processes to promote data quality (e.g., double data entry; range checks for data values).* Reference to where details of data management procedures can be found, if not in the protocol.

Data-input from source documents will be double-checked by 2 persons.

20 Statistical methods

20a: Statistical methods for analyzing primary and secondary outcomes. Reference to where other details of the statistical analysis plan can be found, if not in the protocol.

The primary analyses will compare changes from Month 0 to Month 3 between the exercise group and the waitlist control group. According to guidelines for statistical analysis of clinical trials published by The European Agency for the Evaluation of Medicinal Products (CPMP/ICH/363/96 and CPMP/EWP/2863/99), we will computed the primary statistical analysis for all outcomes using ANCOVA models adjusting for baseline measurements of the respective outcome variable to evaluate treatment effects (measured

as change from baseline). No other covariates will be included in this primary analysis. As recommended, this model will also not include treatment by covariate interactions.

All primary analyses will be conducted as intention-to-treat (ITT) including all patients who have received group allocation. Every effort will be made to obtain Month 3

Wk 0	Mo 3		Mo 6

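### The endpoint sections name one primary endpoint (VLMT, no score given), section 14 sizes the trial for two at two-sided 0.025 each, and section 20a carries neither the two scores nor the 0.025 into the analysis

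*Protocol*

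**What the plan says.** **Endpoint sections: one endpoint.** Section 7 (Objectives) labels verbal learning and memory as the primary endpoint, in the singular. Section 12.1.1 says "The primary endpoint of this study will be the Verbal Learning and Memory Scale", assessed after 3 months of training. Table 2 has a single primary row with VLMT as the measure. None of these places says which VLMT score is meant.

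**Sample size section: two endpoints.** Section 14 calculates separately for VLMT learning (trials 1 to 5) and delayed recall (trial 7). Section 14.1 concludes "Group sample sizes of 20 and 20 achieve 90% power to detect a difference of -5.8", and section 14.2 "Group sample sizes of 17 and 17 achieve 92% power to detect a difference of -2.6". Both statements are made "with a significance level (alpha) of 0.02500 using a two-sided two-sample t-test". The tables also list rows at 0.05, but the text and the chosen 20 per arm use the 0.025 rows. Section 14.3 then describes "powering for the dual primary endpoints VLMT learning and VLMT delayed recall, 90% power will be achieved with n=20 patients in each" arm, and raises enrolment to 60 (about 30 per arm) to cover dropout of up to 20% and a possibly overestimated pilot effect.

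**Analysis section.** Section 20a prescribes the "primary statistical analysis for all outcomes using ANCOVA models adjusting for baseline measurements of the respective outcome variable", comparing change from Month 0 to Month 3. It does not mention two VLMT scores, give a significance level, or say whether one or both scores must be significant.

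**The concern.** The number of primary endpoints differs between the section that defines them and the section that sizes the trial for them. Only the sample size section shows which scores are meant and at what level each would be tested.

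The primary conclusion can depend on which section is followed. Suppose learning gives p = 0.04 and recall is not significant. Someone working from section 12.1.1, with one primary endpoint and the conventional 0.05, could report success. Someone working from section 14, with two endpoints at 0.025, would report failure. A result with one score below 0.025 and the other above it is likewise open, because no either-or-both rule is given. These choices should be closed before the code is broken.

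The power statement has a related ambiguity. Ninety per cent power for dual endpoints can mean power for each, for at least one, or for both, and these differ.

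**Working it through.** **1. Reproduce the plan's power.** Inputs from sections 14.1 and 14.2: learning means 4.0 and 9.8, SD 5.0, so d = 5.8/5.0 = 1.16; recall means 0.6 and 3.2, SD 2.0, so d = 2.6/2.0 = 1.30; two-sided alpha 0.025. For a two-sample t-test with n per arm, df = 2n − 2 and the noncentrality is d × √(n/2). Power is the probability that a noncentral t exceeds the two-sided critical value in absolute size.

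- Learning, n = 20: noncentrality 1.16 × √10 = 3.67; power 0.90388 (plan: 0.90388).
- Recall, n = 17: noncentrality 1.30 × √8.5 = 3.79; power 0.91886 (plan: 0.91886).

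All eight rows of the two tables reproduce to five decimals.

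**2. Family-wise error if either score suffices.** For independent tests it is 1 − (1 − α)²; the upper bound is 2α. For correlated tests it comes from the bivariate normal. The protocol gives no correlation between the scores, so the range below is an assumption.

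| Correlation | 0.025 each | 0.05 each |
|---|---|---|
| 0 | 4.94% | 9.75% |
| 0.5 | 4.65% | 9.07% |
| 0.7 | 4.30% | 8.35% |
| 0.9 | 3.62% | 7.04% |
| Upper bound | 5% | 10% |

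If both scores must be significant, the error cannot exceed the level of a single test, so there is no inflation even at 0.05 each.

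**3. What the 90% covers at 20 per arm, 0.025 each.** Learning has 90.4%. Recall has noncentrality 1.30 × √10 = 4.11 and power 95.8%. Simulation with d = 1.16 and 1.30 gives:

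| Correlation | Both | At least one |
|---|---|---|
| 0 | 86.7% | 99.6% |
| 0.5 | 87.8% | 98.5% |
| 0.7 | 88.8% | 97.6% |
| 0.9 | 90.1% | 96.3% |

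Under independence, 0.904 × 0.958 = 0.866 agrees with the first row. Whatever the correlation, power for both is at least 0.904 + 0.958 − 1 = 0.862.

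**4. At the planned enrolment.** Thirty per arm less 20% leaves 30 × 0.8 = 24. At 0.025, learning has 95.2% and recall 98.4%, so power for both is at least 0.952 + 0.984 − 1 = 0.936. With all 30 per arm the figures are 98.4% and 99.6%, so power for both is at least 98.1% (0.9843 + 0.9963 − 1 = 0.9807).

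**5. Holm compared with 0.025 each, at 20 per arm.** Holm tests the smaller p-value at 0.025 and, if that is significant, the larger at 0.05. It therefore rejects whenever the fixed split does. By simulation, power for learning rises from about 90% to about 94%, and power for both from 87–90% to about 93–94%, with the family-wise error still at most 5%.

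**6. If both are required, each at 0.05, at 20 per arm.** Learning has 94.7% and recall 98.0%. Power for both is about 93% to 95% over the same correlations.

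**The case against.** The strongest defence is that the plan's intention is clear enough. The only level tied to the chosen sample size is 0.025 per score, the scores are identified in section 14, and the 0.05 rows are alternative scenarios like the 80% power rows. Multiplicity procedure and decision rule are often left to a SAP, which is not at hand. Most of this stands: if 0.025 is carried through, the error is controlled. It does not remove the conflict between one and two primary endpoints, which is a matter of what the protocol itself says.

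Four stronger readings are tempting, and the document does not support them:

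- **That the plan runs at about 10% error.** This needs both 0.05 per score and success on either. The protocol states neither.
- **That the success rule is contradictory.** No success rule is given anywhere, so none conflicts with another. What conflicts is the number of primary endpoints.
- **That one ANCOVA model for all outcomes puts the secondary and tertiary endpoints in the primary family.** It does not; Table 2 keeps the hierarchy.
- **That the 90% is wrong or the trial too small.** Read as power for each endpoint, 90% is met (90.4% and 95.8%). It falls short only if read as power for both at 20 per arm, by at most about 4 points, and the planned enrolment covers that.

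Holm is likewise an improvement on offer. The 0.025 split implied by section 14 is not an error.

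**Conclusion.** The point holds as an internal inconsistency about the primary endpoint. Sections 7 and 12.1.1 and Table 2 have one endpoint with no score; section 14 has two at two-sided 0.025 each; section 20a does not settle which applies. The consequence is a primary conclusion that can change with the section followed.

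Its size depends on the reading. Carrying 0.025 forward keeps the family-wise error at or below 5%. Following the single-endpoint wording, testing each score at 0.05 and accepting either gives about 7% to 10% for assumed correlations of 0.9 down to 0. Two scores from one test are probably positively correlated, which would place the figure below the top of that range, but the protocol gives no value.

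The stated 90% is the power for learning alone at 20 per arm. The power figures use the protocol's pilot-based effects, which section 14.3 itself says may be too large, and its t-test rather than the planned ANCOVA. On those assumptions no change in sample size is needed.

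**What to change.** - **Sections 7 and 12.1.1 and Table 2:** name two primary endpoints, the change from Month 0 to Month 3 in VLMT learning (trials 1 to 5) and in VLMT delayed recall (trial 7).
- **Section 20a:** state that the two scores are tested at a two-sided family-wise level of 0.05, either by Holm or at 0.025 each, and that the trial succeeds if at least one is significant. Holm is never less powerful than the fixed split.
- **Section 14.3:** label the 90% as per-endpoint power (learning, 20 per arm, two-sided 0.025).
- **If both scores must be significant:** say so in 20a, test each at 0.05, and replace the power statement with the joint power and the correlation assumed for it.

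The cost is a few sentences of protocol text, settled before the study code is broken. Sample size, assessments and analysis model are unchanged. Section 27 requires approval by the monitoring board for major changes such as those to outcome measures, and submission of amendments to the ethics committee, so the clarification should follow that route.

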Management of screening, inclusion and study conduct will be based on the internet-based project-management tool attached to the HAPIMS database. This database uses secure data management and has been approved for use by the responsible Data Protection and Security Office of the UKE. Data will be collected on paper-based source documents (neuropsychological assessments, performance-based measures, questionnaires) or primary computer-based (MRI, MEG) or chip-based (accelerometry). Data will be uploaded on a protected web-based project-platform to allow an integrated view on all assessments.

Assessment of safety: DSMB reports will be prepared biannually. As we do not expect adverse events DSMB recommendations for taking patients out or stopping the study seem highly unlikely.

18b Retention: Plans to promote participant retention and complete follow-up, including list of any outcome data to be collected for participants who discontinue or deviate from intervention protocols.

See 11c.

19 Data management: *Plans for data entry, coding, security, and storage, including any related processes to promote data quality (e.g., double data entry; range checks for data values).* Reference to where details of data management procedures can be found, if not in the protocol.

Data-input from source documents will be double-checked by 2 persons.

20 Statistical methods

20a: Statistical methods for analyzing primary and secondary outcomes. Reference to where other details of the statistical analysis plan can be found, if not in the protocol.

The primary analyses will compare changes from Month 0 to Month 3 between the exercise group and the waitlist control group. According to guidelines for statistical analysis of clinical trials published by The European Agency for the Evaluation of Medicinal Products (CPMP/ICH/363/96 and CPMP/EWP/2863/99), we will computed the primary statistical analysis for all outcomes using ANCOVA models adjusting for baseline measurements of the respective outcome variable to evaluate treatment effects (measured

as change from baseline). No other covariates will be included in this primary analysis. As recommended, this model will also not include treatment by covariate interactions.

All primary analyses will be conducted as intention-to-treat (ITT) including all patients who have received group allocation. Every effort will be made to obtain Month 3

Wk 0	Mo 3		Mo 6
Outcome assessments	ks of training Outcome assessments	Continue training	Outcome assessment
SECONDARY ANAL	YSIS (3 Mo Exercise vs 6 I	Mo Exercise vs Natu	ral History) ^{Mo 6}
Wk 0		Mo Exercise vs Natu Continue training	• •
Wk 0	Mo 3 ks of training Outcome assessments	Continue training 12 weeks of training	Mo 6 Outcome

and Month 6 data from all participants (even if they drop out of the exercise program). However, in case of missing data, primary ITT analyses will be conducted using a Last-Observation-Carried-Forward (LOCF) approach.

As sensitivity analyses, we will compute the same ANCOVA models as per-protocol (i.e. including only patients who completed the 12 weeks of training with at least 2 sessions in each week) as well as non-

parametric intent-to-treat (ITT) analyses using Kruskal-Wallis tests where patients who drop out are assigned the lowest rank.

20c: Definition of analysis population relating to protocol nonadherence (e.g., asrandomized analysis), and any statistical methods to handle missing data (e.g., multiple imputation)

Data analysis will be ITT as well as PP. For ITT analyses, missing data will be handled using a Last-Observation-Carried-Forward (LOCF) approach.

21: Monitoring

21a: Composition of DMC; summary of its role and reporting structure; statement of whether it is independent from the sponsor and competing interests; and reference to where further details about its charter can be found, if not in the protocol. Alternatively, an explanation of why a DMC is not needed.

Monitoring will be through biannual reporting to the Neu2 Steering committee.

21b: Description of any interim analyses and stopping guidelines, including who will have access to these interim results and make the final decision to terminate the trial Not planned.

22 Harms: Plans for collecting, assessing, reporting, and managing solicited and spontaneously reported adverse events and other unintended effects of trial interventions or trial conduct

Based on the literature as well as own study experiences especially in progressive MS patients, we do not expect adverse events: However, some patients might experience temporary worsening of symptoms which might lead to adjustment of the training.

23 Auditing: Frequency and procedures for auditing trial conduct, if any, and whether the process will be independent from investigators and the sponsor

There are no in advance planned audits. However, regulatory authorities might choose to audit the study.

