In addition to imaging makers of brain structure and connectivity, we will analyze several domains of *higher-order brain function* as secondary endpoints. These include attention (Test of Attentional Performance, TAP), visuospatial learning and memory (Brief Visuospatial Memory Test Revised, BVMT-R, Benedict et al. 1997), processing speed (Symbol Digit Modalities Test, SDMT, Smith 1973, Paced Auditory Serial Addition Task, PASAT, Gronwall, 1977), working memory (Corsi Block, Corsi 1972), and social cognition (theory of mind as determined by the Movie for Assessment of Social Cognition, Dziobek et al., 2006). Cognitive function is of major clinical importance in MS since is linked to quality of life and vocational status. In addition, currently available disease-modifying therapies have limited effects on cognition and attempts to develop pharmacological therapies for cognitive impairment have been unsuccessful in MS (Benedict & Zivadinov Nat Rev Neurol 2011). Therefore, exploring novel treatment options for cognitive dysfunction in MS such as exercise is highly relevant for MS care.

12.1.3. Tertiary endpoints:

Tertiary outcomes include objective measures of *walking ability*. We will obtain total distance (in meters) during the six-minute walk test (6MWT) as well as "real-life" walking speed as measured by the Actibelt® over the course of 7 days.

Furthermore, we will obtain patient-reported outcome measures (PRO) to assess subjective well-being and quality of life. These measures include the Inventory of Depressive Symptoms (IDS-30SR), the Fatigue Scale for Motor and Cognitive Function (FSMC, Penner et al., 2009), the Hamburg Quality of Life Questionnaire for Multiple Sclerosis (HAQUAMS, Gold et al., 2001), and the Multiple Sclerosis Walking Scale-12 (MSWS-12, Hobart et al.)

Finally, we will objectively assess motor coordination and balance using the MFT-S3.

12.2. Ancillary studies:

In order to maximize the scientific insight that can be gained from this phase IIa trial with respect to the neurobiology and physiology of exercise in multiple sclerosis, we will conduct a series of ancillary studies that address potential biomarkers, changes in CNS pathology, aerobic fitness and metabolic effects on fat and muscle tissue as well as psychological factors that might influence treatment response and adherence.

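### The rank-based sensitivity analysis gives dropouts the lowest rank whatever the scale direction; read literally, that is the best rank on the tertiary depression and fatigue scales

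*Protocol*

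**What the plan says.** Section 20a sets out the "primary statistical analysis for all outcomes using ANCOVA models adjusting for baseline measurements of the respective outcome variable", by intention to treat, with missing values filled by last observation carried forward. Two sensitivity analyses follow. One repeats the ANCOVA per protocol. The other is a rank-based intention-to-treat analysis "using Kruskal-Wallis tests where patients who drop out are assigned the lowest rank". The rank analysis has no outcome list of its own, and nothing is said about scale direction or recoding.

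Section 7 places "patient-based outcomes (depression, fatigue, and health-related quality of life" among the tertiary outcomes. Section 12.1.3 names the instruments: "These measures include the Inventory of Depressive Symptoms (IDS-30SR), the Fatigue Scale for Motor and Cognitive Function", followed by quality-of-life and walking scales. The protocol does not state how any of them is scored.

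Section 20a promises every effort to obtain Month 3 "and Month 6 data from all participants (even if they drop out of the exercise program", so there the words refer to leaving the training. The rank rule does not say whether it uses them in the same sense. On the amount of dropout, Section 14.3 says that "drop-out in behavioral trials often reach 20" per cent. No figure by arm is given.

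**The concern.** The rank analysis is the only planned analysis that counts dropout as a bad outcome. Last observation carried forward scores a patient without a Month 3 value as unchanged, and the per-protocol analysis leaves out patients who did not complete training. Its value lies in that penalty.

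The penalty works only where a low value is a poor result. On a symptom scale where high is worse, ranking upwards and placing dropouts at the bottom gives them the best result in the trial. The arm that loses more patients then looks better, and a true worsening can disappear. Unequal loss is plausible: Section 11c allows exclusion for interrupted or reduced training and provides for exclusion when symptoms persistently worsen after sessions. Before Month 3 only the exercise arm can meet those conditions.

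The undefined term adds to this. If dropping out means leaving the exercise programme, only exercise patients can do it before Month 3. Observed Month 3 values would then be overwritten by a rank in one arm only.

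**Working it through.** **The plan's own figure.** Section 14.1 gives power 0.90388 for VLMT learning (20 per arm, difference 5.8, SD 5.0, two-sided alpha 0.025). The noncentral t distribution returns 0.90388. This point does not bear on that figure.

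**Inputs.** From the protocol: 60 patients, about 30 per arm; dropout of 20%, that is 12 of 60; Kruskal-Wallis test. Assumed: high score is worse; the splits of dropouts by arm; two-sided 0.05 (so 2.5% in each direction); normal scores; dropout unrelated to the score; all dropouts tied at one extreme.

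**Direction by arithmetic.** Let D be total dropouts, with dE in exercise and dW in waitlist. At the lowest rank, dropouts share mean rank (D + 1)/2 and the others average (D + 61)/2, a gap of 30. With no true effect, the expected mean rank of an arm with d dropouts is [d(D + 1)/2 + (30 − d)(D + 61)/2]/30. The arms therefore differ by 30(dE − dW)/30 = dE − dW.

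For 8 v 4:
- exercise: (8 × 6.5 + 22 × 36.5)/30 = 855/30 = 28.5
- waitlist: (4 × 6.5 + 26 × 36.5)/30 = 975/30 = 32.5

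Exercise ranks 4 places lower, which on a symptom scale means better, with no true effect. At 6 v 6 the difference is 0.

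**No true effect, 20,000 simulated trials per setting**

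| Dropouts, exercise v waitlist | Lowest rank: significant for exercise | Worst rank: significant against exercise |
|---|---|---|
| 6 v 6 | 0.2% | 0.2% |
| 7 v 5 | 1.7% | 1.7% |
| 6 v 3 | 4.8% | 4.9% |
| 8 v 4 | 6.7% | 6.8% |
| 9 v 3 (assumed extreme) | 19% | 19% |
| 6 v 0 (assumed extreme) | 23% | 23% |

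With complete data the share favouring exercise is 2.4%. A separate simulation with 4,000 trials per setting gave 0.3% at 6 v 6, 4.7% at 6 v 3 and 23% at 6 v 0 for the lowest rank.

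**True worsening of 0.5 SD under exercise: share of trials that find the harm**

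| Setting | Lowest rank | Worst rank |
|---|---|---|
| Complete data | 45% | 45% |
| 6 v 6 | 12% | 13% |
| 8 v 4 | 0.4% | 57% |

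With equal dropout the wording makes no difference. At 8 v 4 it decides whether the harm is seen. The 57% exceeds the complete-data 45% because the worst rank also counts the extra exercise dropouts against exercise.

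**The case against.** Giving dropouts the lowest rank is normally meant as a penalty, and the endpoint on which the trial is powered fits that sense: VLMT improves upwards. The natural reading is therefore the worst rank. Application to the tertiary scales is also inferred. The phrase on all outcomes belongs to the ANCOVA, and the prompt that opens 20a reads "Statistical methods for analyzing primary and secondary outcomes", with no mention of tertiary ones. Scale direction is not in the protocol at all, and orienting ranks by scale could be left to an analysis plan. Finally, at 20% dropout the two most even splits show no inflation.

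Most of this stands, and it keeps the point minor. It does not remove it. The protocol is not silent here: it states a concrete rule, and that rule gives the wrong result if programmed as written on a scale where high is worse. The rank analysis follows an analysis set for all outcomes and is not restricted to some of them.

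A reader might infer more than the protocol supports:
- **That the primary result is compromised.** It is not. The primary VLMT analysis is an ANCOVA, and in the rank analysis of VLMT the lowest rank is the worst.
- **That false-positive rates near 20% are to be expected.** Those figures need 9 v 3 or 6 v 0, and the protocol gives no dropout by arm.
- **That the correction lowers the error rate.** It reverses the sign of the null error without reducing its size.
- **That the sponsor meant to reward dropout.** Nothing in the protocol suggests this.

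**Conclusion.** A minor wording error in one of two sensitivity analyses. Taken literally, the rule favours the arm with more dropouts on IDS-30SR and FSMC, with about 5% to 7% false benefit at 6 v 3 or 8 v 4 against a nominal 2.5%, and none above nominal at 6 v 6 or 7 v 5. It could also mask a worsening.

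The conclusion rests on four conditions together: a literal reading of the rule, a scale direction taken from the instruments' names, a scope that extends to tertiary outcomes, and dropout of roughly 2:1. The sponsor probably meant the worst rank. Sample size, alpha and all ANCOVAs are untouched. Confidence is medium, because the conditions are plausible but not stated.

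**What to change.** Replace the rank rule in Section 20a with a sentence such as:

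> Patients without a Month 3 value are assigned the worst rank in the direction of the scale (lowest for VLMT and 6MWT; highest for IDS-30SR, FSMC and other scores where high is worse), by the same rule in both arms. Patients who left training but were assessed at Month 3 keep their observed value.

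The sponsor should confirm each scale's direction from its scoring rules. The second sentence settles who counts as a dropout in a way that suits an intention-to-treat analysis. If the intention was to score leaving training as failure, the protocol should say so and accept that this can affect only the exercise arm before Month 3.

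The cost is one sentence and no new data. The downside is that worst-rank scoring deliberately penalises the arm with more missing values: with no true effect, significance against exercise is 4.9% at 6 v 3 and 6.8% at 8 v 4. The plan already accepts this for VLMT.
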